#### **Interim Analysis**

Interim analysis for primary and secondary outcomes, as well as safety parameters, will be performed upon completion of 50% of the total recruitment. If statistically significant superiority of either arm is identified, the trial will be terminated.

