#### **Trial Design**

This study will be carried out as a prospective, randomized, single-blinded clinical trial.

The intervention group will receive intraoperative laparoscopically assisted, surgeon-placed TAP blocks using 1mL/kg of 0.25% bupivacaine with epinephrine 1:200,000 combined with 16mg dexamethasone divided into 4 aliquots to be placed at two locations per side along the anterior axillary line between the

costal margin and the iliac crest. The control group will have TAP blocks with the same dose of bupivacaine without dexamethasone. The blocks will be performed at the conclusion of surgery. Postoperatively, all patients will be provided with patient-controlled analgesia (PCA) with institutional standardized orders.

Intravenous dexamethasone will not be given for prevention of postoperative nausea and vomiting (PONV); prophylaxis of postoperative nausea and vomiting will be at the discretion of the anesthesiologist, but can include any of ondansetron, haloperidol, or dimenhydrinate. If PONV occurs and is refractory to non-corticosteroid treatment, dexamethasone may be given for treatment but would result in exclusion from the trial. General anesthetic technique will be at the discretion of the anesthesiologist, but the following adjunct anesthetic drugs will not be permitted, due to independent effects on postoperative pain: dexmedetomidine, lidocaine, and ketamine. These adjuncts are occasionally used in anesthetic protocols, but their exclusion will not affect the quality of the anesthetic provided, and their use is not considered standard of care. All patients will be provided with a standardized hydromorphone-based patient-controlled analgesia (PCA) for a minimum of 48 hours postoperatively.

The primary outcome will be total opioid consumption, in hydromorphone equivalents, in the first 48 hours after surgery. Secondary outcomes will be length of stay in the post-anesthetic care unit (PACU), length of stay in hospital, and total opioids administered in the PACU.

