#### **Stopping Criteria**

Interim analysis will be performed after 50% enrolment. If either arm is found to be superior, the trial will be discontinued. If any adverse events are identified in either arm, a safety review will be performed. Should a significant safety concern be identified, the trial will be discontinued.

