#### Selection and withdrawal of subjects

We intend to enroll a sample size of 120 patients based on an alpha set at 0.05, power set at 0.08, and the effect size set at 0.8.

Inclusion criteria are: age > 18, ASA class I-III patients scheduled for elective or urgent inpatient laparoscopic/laparoscopic assisted colorectal surgery.

Exclusion criteria are: emergency surgery, open surgery, contraindications to laparoscopic surgery (ie. adhesions, inability to tolerate pneumoperitoneum), ASA class  $\geq 4$ , age < 18, pregnant or breastfeeding women, significant cardiorespiratory/hepatic/renal disease, allergy to any study drugs, inability to consent, inability to respond to pain assessments, inability to use the patient-controlled analgesia device (PCA), preoperative chronic opioid use.

Potential participants will be identified by their attending surgeon during their initial clinic surgical consultation. This typically occurs several weeks in advance of their scheduled surgical procedure. Information detailing the study, as well as contact information of the research team will be made available to patients at this time should they have any questions. After having had a chance to review the study information provided to them by their surgeon, prospective patients will be assessed by study staff (attending surgeon or designate such as a general surgery resident) and asked to sign a consent if they agree to participate and meet the inclusion criteria. The consent will be taken on the day of surgery.

Participants who are unable to personally provide informed consent will be excluded from the study. No third party will be allowed to consent on the participants behalf. Capacity will be assessed by the study staff or designate obtaining consent. All patients participating must be assessed to determine that they fully understand the protocol, risks, and benefits of participating in the study.

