#### **Assessment of efficacy**

The primary efficacy outcome of this study will be total opioid consumption, in hydromorphone equivalents, at 24 and 48 hours postoperatively. Secondary outcomes will be length of stay in the post-anesthetic care unit (PACU), length of stay in hospital, and total opioids administered in the PACU.

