#### **Statistics**

Primary Outcome:

Total opioid consumption at 24 and 48 hours will be gathered from the PCA record and Medication Administration Record (MAR). Intention to treat analysis will be performed. Parametric data will be analyzed with the students t-test for statistical significance.

Secondary Outcome: Opioid consumption in the PACU will be reported in hydromorphone equivalents and compared with chi square test. Length of stay in PACU and length of stay in hospital will be reported as a mean +/- standard deviation (SD), along with confidence intervals and compared with chi square test.

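### The half-way efficacy stop has no boundary, no adjusted final level and no named trigger outcome; two looks at 0.05 on the primary outcome alone give a type I error of 8.3%, not 5%

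*Protocol*

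**What the plan says.** The Protocol fixes the efficacy stop in two places. Interim Analysis sets the timing and content of the look: "Interim analysis for primary and secondary outcomes, as well as safety parameters, will be performed upon completion of 50% of the total recruitment". It then gives the rule: "If statistically significant superiority of either arm is identified, the trial will be terminated". Stopping Criteria has the same rule in other words: "If either arm is found to be superior, the trial will be discontinued". Both are mandatory, and neither names a significance level, a boundary or an outcome.

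The only significance level in the Protocol is in the sample-size sentence (Selection and withdrawal of subjects): "a sample size of 120 patients based on an alpha set at 0.05". The Statistics section names the tests (Student's t-test for the primary outcome, chi-square for the secondary outcomes) and no level for either look.

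The time point of the primary outcome also varies. Trial Design says: "The primary outcome will be total opioid consumption, in hydromorphone equivalents, in the first 48 hours after surgery", and Trial Objectives and Purpose agrees. Assessment of efficacy says: "The primary efficacy outcome of this study will be total opioid consumption, in hydromorphone equivalents, at 24 and 48 hours postoperatively". Under the primary-outcome label, Statistics says: "Total opioid consumption at 24 and 48 hours will be gathered from the PCA record".

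**The concern.** Testing at half-way and again at the end gives two chances to declare a difference that does not exist. Unless the two levels are set jointly, the overall error rate exceeds the nominal one. The Protocol describes the interim criterion only as statistical significance, and 0.05 is the only level it offers.

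The trigger is also open. Several outcomes are analysed at the interim and the stopping sentence follows without choosing among them. A reader cannot tell whether a difference in PACU stay alone would end a trial designed around 48-hour opioid use. Saying that the primary outcome decides would not settle it either, because one section gives that outcome a single time point and another gives it two.

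The Protocol calls the trial a proof of concept that will guide work on dosing and a comparison with systemic dexamethasone. A false positive, or an effect exaggerated by an early stop, would carry straight into those designs. Once recruitment has been ended on such a rule, the decision cannot be repaired in the analysis.

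**Working it through.** **Inputs from the Protocol.** Alpha 0.05; effect size 0.8, read as a standardised difference; 60 per arm, 1:1; one interim at 50% of recruitment, so 30 then 60 per arm. Superiority of either arm implies a two-sided test. There is no stated interim error rate to reproduce.

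**Assumptions.** Statistical significance means two-sided p < 0.05 at each look. The information fraction at the interim is 60/120 = 0.5. Simulations use normal data with SD 1.

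**1. Type I error, 48-hour primary outcome only.** Under no effect, the test statistics Z1 and Z2 are bivariate normal with correlation √0.5 = 0.707.

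- Error = 1 − P(|Z1| < 1.96 and |Z2| < 1.96) = 1 − 0.9169 = 0.0831.
- Of this, 0.0500 arises at the interim and 0.0331 from trials that first reach significance at the end.
- Simulated t-tests (30 then 60 per arm, one million trials) give 0.0830.
- With one-sided 0.05 at each look, the figure is 8.0%.

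The normal-theory figure does not depend on the SD, the effect size or N.

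**2. If any outcome could trigger the stop (illustrative).** With k independent outcomes each tested at 0.05, the chance of a false interim stop is 1 − 0.95^k.

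| Outcomes | Independent | Assumed common correlation 0.8 |
|---|---|---|
| k = 4 (48 h opioids, PACU opioids, PACU stay, hospital stay) | 18.5% | 11.5% |
| k = 5 (adding 24 h opioids) | 22.6% | 12.7% |

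These use normal statistics, not the planned chi-square tests. A stop on a secondary outcome is not a false positive on the primary.

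**3. Boundaries that restore 5%.** Each was solved from the same bivariate normal distribution.

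| Boundary | At 60 patients | At 120 patients |
|---|---|---|
| O'Brien-Fleming | z = 2.797, p < 0.0052 | z = 1.977, p < 0.048 |
| Haybittle-Peto | p < 0.001 | z = 1.962, p < 0.0498 |

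Simulated overall type I error is 0.0498 and 0.0497 respectively.

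**4. Behaviour when there is an effect.** The 0.8 SD is the Protocol's; 0.5 SD is an assumption. Expected enrolment = 120 − 60 × P(stop).

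| | 0.8 SD, plain 0.05 | 0.8 SD, O'Brien-Fleming | 0.5 SD, plain 0.05 | 0.5 SD, O'Brien-Fleming |
|---|---|---|---|---|
| Stops at interim | 86% | 58% | 48% | 18% |
| Mean estimate given a stop (SD) | 0.87 | 0.97 | 0.71 | 0.87 |
| Overall power | 99.3% | 99.1% | 79.8% | 77.2% |
| Expected enrolment | 68 | 85 | 91 | 109 |

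A single fixed t-test with 120 patients has power 99.1% at 0.8 SD and 77.5% at 0.5 SD. Under the plain rule, overestimation after a stop is 0.87/0.8 − 1, about 8%, at 0.8 SD, and 0.71/0.5 − 1, about 42%, at 0.5 SD.

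**The case against.** Interim boundaries are often set in a statistical analysis plan, which is not available here. The 0.05 appears once, in the sample-size sentence, and can be read as the overall level. Strictly, then, the rule gives no level at all, and 8.3% is the consequence of a reading. It is the natural reading, though. The Protocol does more than leave the boundary open: it states a mandatory stop twice, in unadjusted terms. A later boundary would have to narrow the Protocol's own wording.

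The figures for several outcomes rest on a reading that the text permits but does not state, on assumed correlations and on normal statistics. They illustrate why the trigger needs a name, and the case does not depend on them.

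The 24- versus 48-hour discrepancy is a defect in its own right, and the Statistics sentence may describe only data collection. It still matters here, because a stopping rule needs one trigger.

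The strongest point concerns overestimation, because a stricter boundary does not cure it. Conditional on stopping, inflation grows, as the table shows. Averaged over all trials, the mean estimate moves from 0.83 to 0.85 SD at a true 0.8 SD, and from 0.55 to 0.53 SD at a true 0.5 SD. This stands: the case for the boundary is control of type I error, and overestimation needs its own remedy. The cost in patients is also real and is stated under the fix.

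Finally, 8.3% instead of 5% may seem moderate in a proof-of-concept trial. The Protocol nevertheless sets 0.05 as its standard, and the correction is cheap.

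**Conclusion.** The concern holds. The Protocol fixes a binding efficacy stop without a boundary, an adjusted final level or a trigger outcome. Read with the only level it gives, two-sided at both looks and at half the information, the rule has a type I error of 8.3% on the 48-hour primary outcome, about 1.7 times the stated 5%. If secondary outcomes may also trigger the stop, the chance of a false interim stop is roughly 11% to 23%, depending on the number of outcomes and the assumed correlation. Early stopping is the likely course under the Protocol's own effect size, so inflation of the estimate is a practical matter, about 8% at 0.8 SD and more if the true effect is smaller. This must be corrected before the interim analysis is carried out.

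**What to change.** In Stopping Criteria and Interim Analysis:

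- Name total opioid consumption in the first 48 hours as the only outcome that can trigger an efficacy stop, and state that secondary outcomes cannot.
- State the boundary and the final level, two-sided. Examples are O'Brien-Fleming (p < 0.0052 at 60 patients, p < 0.048 at 120) or Haybittle-Peto (p < 0.001, then p < 0.0498).
- Require a bias-adjusted estimate, or an explicit caution about overestimation, if the trial stops early.
- Leave the safety review as it is.

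Align Assessment of efficacy and Statistics with Trial Objectives and Purpose and Trial Design on the 48-hour time point, keeping the 24-hour total as a supporting measure if it is wanted.

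The cost is a few sentences. Against a single fixed test with 120 patients, O'Brien-Fleming power is 77.2% versus 77.5% at 0.5 SD, and equal to rounding (99.1%) at 0.8 SD. Against the present rule, early stops become rarer and expected enrolment rises by about 17 patients at 0.8 SD (68 to 85) and 18 at 0.5 SD (91 to 109). The maximum stays at 120.

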#### Direct access to source data / documents

The Investigator acknowledges that some authorities have a duty to monitor the study records to make sure all the information is correct. The study records may be inspected in the presence of the investigator or his qualified designate by representatives of Health Canada or the University of Saskatchewan Biomedical Research Ethics Board for quality assurance and/or regulatory purposes.

#### **Quality Control and Quality Assurance Procedures**

Patients will be monitored intraoperatively by a qualified staff anesthesiologist. Following surgery, patients will be extubated fully awake in the operating room and transferred to the PACU with supplemental oxygen. In PACU patients will be monitored by dedicated nursing staff and will have access to nurse-administered analgesia. Standard antiemetics will be available as well, and dexamethasone can be given systemically as a rescue antiemetic. If this occurs, the patient will be excluded from the study. Following discharge from PACU, patients will be monitored on the ward by nursing staff and postoperative care will be administered as per usual protocol.

#### **Ethics**

The Investigator will ensure that this study is conducted in full compliance with the principles of the Declaration of Helsinki and with the laws and regulations in Canada. This clinical study will be implemented and reported in accordance with the ICH Harmonized Tripartite Guidelines for Good Clinical Practice.

This study (including protocol and proposed consent form) has been submitted to the University of Saskatchewan Biomedical Research Ethics Board. Eligible subjects will only be included in the study after providing written BREB-approved consent.

#### Data handling and record keeping

All information collected on the data collection form will be de-identified and no direct personal identifiers will be recorded. All measures will be taken to maintain confidentiality on collected data; however, there is a chance of unintentional release of information connecting the subject with the study. A list connecting

the subject's name to the subject study number listed on the data collection form will be stored in a password-protected computed kept in the locked office of the principal investigator, located at Royal University Hospital, Saskatoon. Access to this list will be limited to study staff, and it will be destroyed upon study completion through the confidential paper shredding services of the Royal University Hospital.

Data will be stored for 25 years, as per the Health Canada requirements. The Investigator is responsible to archive the documents/data for the required period of time.

#### **Financing**

This study has received funding of \$10,000 from the Department of Surgery, University of Saskatchewan.

